13.1.4 Interim analysis

An interim analysis on efficacy will be performed after the first peak transmission season, approximately in December 2018. The same efficacy analysis methods will be applied to the interim analysis in both ITT and per protocol cohorts. The interim analysis will be performed to assist regimen selection in future studies. The analysis results will not affect the final analysis of the study. The interim analysis will be completed by the study statistician. Analysis will be reviewed by LMIV senior investigator and PI, MRTC senior investigator, the sponsor and DSMB. Subjects, site clinicians and site personnel conducting clinical assessments and LMIV

and MRTC laboratory personnel conducting study related assays will remain blinded until after scheduled unblinding at the completion of the study.

13.2 Sample Size Consideration

Sample size consideration is primarily based on VE evaluation. Seventy subjects will be enrolled in each arm. If the annual drop-out rate is between 15% and 28%, there will be 50 to 60 available subjects for efficacy evaluation at one year after study initiation. With 50 samples per arm, the study is capable of detecting the protective efficacy of vaccine with 88% power if VE is 45% and the background infection rate is 0.7 (see [Table 8](#)). With 60 samples per arm, the study has 83% power if VE is 45% and background infection rate is 0.6. For safety evaluation, with 70 subjects in each arm, there is 90% probability of observing at least one AE in the arm if the adverse event rate is no less than 0.033.

Based on data from existing studies, the number of participants in the booster phase will be close to that in the main phase. The above sample size consideration should approximately apply to the booster phase.

Table 8: Power for group-wise comparison based on logrank test on time to infection

Sample Size per Arm	Background Infection Rate	Vaccine Efficacy (VE)	Power
50	0.6	0.45	76
50	0.6	0.3	44
50	0.6	0.25	33
50	0.7	0.45	88
50	0.7	0.3	59
50	0.7	0.25	45
60	0.6	0.45	83
60	0.6	0.3	51
60	0.6	0.25	39
60	0.7	0.45	93
60	0.7	0.3	67
60	0.7	0.25	52
70	0.6	0.45	89
70	0.6	0.3	57
70	0.6	0.25	44
70	0.7	0.45	96
70	0.7	0.3	73
70	0.7	0.25	59

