3 STUDY DESIGN

This study will enroll healthy Malian adults between 18 and 35 years of age to participate in a randomized double blind, placebo-controlled study to assess the safety, immunogenicity and protective efficacy of boosting during the second transmission season. Participants will be immunized with a 3-dose series of 9×10^5 PfSPZ Vaccine (cryopreserved radiation attenuated *P. falciparum* sporozoites via DVI) at 0, 8 and 16 weeks interval or 0, 1 and 4 weeks starting during the dry season (see [Figure 5](#)). Vaccinated subjects and controls will then be assessed for malaria infection during the ensuing malaria transmission season. Volunteers will be randomized into four arms. Arms 1 and 3a will be randomized first in a 2:1 ratio. Arms 2 and 3b will be randomized into a 2:1 ratio a few weeks later.

At the completion of the follow up phase after the primary series, participants who received all three vaccine doses and are still enrolled in the study will be invited to continue participation in the study to receive a booster vaccine dose. This 4th dose will be administered prior to the beginning of the following transmission season, approximately 10 months post the 3rd vaccination. Those enrolled in the vaccine arms (*Arms 1 and 2*) will receive one injection of 9×10^5 PfSPZ while those participants enrolled in the control arms (*Arms 3a and 3b*) will receive one injection of normal saline. The study will be maintained blinded as the participants transition from the main phase to the booster phase. Vaccinated subjects and controls will then be assessed for malaria infection during the ensuing malaria transmission season.

Figure 5: Study Schema

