3.1 Study Groups

Arm 1: (n=70) will receive 3 doses of PfSPZ Vaccine (9×10^5) via DVI at 0, 8, and 16 weeks in the main phase, booster dose at 38 weeks post 3rd vaccination.

Arm 2: (n=70) will receive 3 doses of PfSPZ Vaccine (9×10^5) via DVI at 0, 1 and 4 weeks in the main phase, booster dose at 38 weeks post 3rd vaccination.

Arm 3a: (n=35): Will be the control for Arm 1. Volunteers will receive 3 doses of placebo saline injection via DVI at 0, 8 and 16 weeks in the main phase, booster dose at 38 weeks post 3rd vaccination.

Arm 3b: (n=35): Will be the control for Arm 2. Volunteers will receive 3 doses of placebo saline injection via DVI at 0, 1 and 4 weeks in the main phase, booster dose at 38 weeks post 3rd vaccination.

All injections will be administered by DVI. All volunteers will receive antimalarial treatment with artemether/lumefantrine (AL) two weeks prior to 3rd injection. Post 3rd injection, participants will be followed through the rainy transmission season, approximately six months. Participants will be monitored for safety, immunogenicity, malaria infection and disease during the follow-up period.

Participants enrolled in the booster phase of the study, at the end of the prior transmission season, will also receive antimalaria treatment with artemether/lumefantrine (AL) at least two weeks prior to booster injection (4th injection overall). Post 4th injection, participants will be followed through the rainy transmission season, approximately six months. Participants will be monitored for safety, immunogenicity, malaria infection and disease during the follow-up period.

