4.4 Sample Size and Estimated Duration of the Study

A total of 210 volunteers will be enrolled/randomized in this trial, 70 subjects in each arm vaccine arms (Arm 1 and 2) and 35 subjects in each control arms (Arm 3a and 3b). A total of 140 subjects will receive PfSPZ Vaccine and 70 will only receive placebo.

Definitions for the purpose of this study:

- **Screened** – subjects will receive a study screening number when the informed consent is signed and will either be determined as “eligible” or “screen failure” as noted below.
 - Screening may be completed over the course of multiple visits.
 - Screening, in most cases, will occur within 56 days prior to administration of vaccine #1.
 - If the screening visit is >56 days administration of vaccine #, then an updated medical review and laboratory testing (CBC, ALT, Creatinine, ECG, Urinalysis, Pregnancy test (for females) will be completed to determine eligibility for enrollment.
 - **Note:** HIV, Hepatitis B, Hepatitis C and ECG are to be repeated during booster phase screening **ONLY IF** clinically indicated
- **Eligible** - subjects will be considered eligible to enroll once they have completed the screening procedures and have **met all inclusion** and **not met exclusion** criteria.
- **Screen Failure** – subjects are considered screen failures when they meet one of the following criteria after signing consent:
 - Screening results reveal that the subject is ineligible.
 - Subject withdraws consent before being vaccinated and/or randomized.
 - Subject cannot present to clinic for enrollment prior to study completing enrollment.
 - Subject is determined eligible for enrollment after study completes enrollment.
- **Randomized** – the subjects are considered randomized when they meet the following criteria:
 - Meet eligibility criteria.

- Study identification number (ID) assigned.
- Randomization number assigned.
- **Enrolled** – In the main phase, subject will be considered enrolled beginning with the collection of baseline labs on study Day -14.
 - In the booster phase, subject will be considered enrolled beginning with the receipt of artemether/lumefantrine prior to receiving 4th vaccination
 - Subjects enrolled in main phase but have not received the first vaccination may be replaced up to the accrual ceiling set for the study.
- **Discontinued/Withdrawn** – subjects are considered discontinued when they meet one or more of the following criteria:

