13 STATISTICAL CONSIDERATIONS

13.1 Endpoints and Statistical Methods

13.1.1 Safety analysis

Safety will be assessed by line listing and tables at the individual level. Intention-to-treat (ITT) group comparisons, between the vaccine arms and the control arm, will be performed in terms of the proportions of solicited AE, related AE and SAE. Other concerning trends will be investigated as needed or requested by the PI, ISM, IND sponsor, and/or DSMB.

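### Table 8's power assumes equal arms, but each regimen's named control arm is half the size of its vaccine arm, and the efficacy section does not say which control is used

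*Combined protocol and SAP*

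**What the plan says.** Section 13.2 opens its calculation with "Seventy subjects will be enrolled in each arm". It applies 15% to 28% annual dropout to reach 50 to 60 evaluable subjects. It then quotes 88% power for 50 per arm (VE 45%, background infection rate 0.7) and 83% for 60 per arm (VE 45%, rate 0.6). Table 8 gives one sample size per arm in each row. The section carries the same reasoning over to the booster phase.

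The design sections describe something else:
- Section 4.4: "70 subjects in each arm vaccine arms (Arm 1 and 2) and 35 subjects in each control arms (Arm 3a and 3b", for a total of 210.
- Section 3.1: "Arm 3a: (n=35): Will be the control for Arm 1" and "Arm 3b: (n=35): Will be the control for Arm 2".
- Section 3: "Arms 1 and 3a will be randomized first in a 2:1 ratio". Arms 2 and 3b follow some weeks later at the same ratio.

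The analysis sections do not settle the comparator. Section 13.1.2 says that arms are compared by an interval-censored log-rank test, with VE stratified by village. It mentions neither pooling of 3a and 3b nor pairing of each regimen with its own control. Section 13.1.1 speaks of comparisons "between the vaccine arms and the control arm", in the singular. Section 13.1.4 adds a purpose: "The interim analysis will be performed to assist regimen selection in future studies".

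**The concern.** Four arms of 70 would make 280 subjects, not 210, so the sentence in Section 13.2 cannot describe all four arms. If each regimen is compared with the control that Section 3.1 assigns to it, the comparison is 2:1 with at most 35 controls, and Table 8 overstates its power. If 3a and 3b are pooled instead, the sample size fits. However, half of that control group was randomised in the other cohort, at another time and on another injection schedule, and no cohort stratum is planned.

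What is at stake is how a null or borderline result for one regimen is read, in both phases. The interim efficacy results also feed regimen selection. Arms 1 and 2 were not randomised against each other, so the randomised evidence on each regimen is the contrast with its own control.

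**Working it through.** **Inputs.** Enrolment is 70 vaccine and 35 control per regimen (Sections 3.1, 4.4). Dropout is 15% to 28% (Section 13.2): 70 × 0.85 = 59.5 and 70 × 0.72 = 50.4; 35 × 0.85 = 29.8 and 35 × 0.72 = 25.2. The evaluable pairs are therefore about 60:30 and 50:25. VE and background rate come from Table 8. Alpha and sidedness are not stated; two-sided 5% is assumed.

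**Reproducing Table 8.** Take VE as 1 minus the risk ratio. With background rate p, the vaccine-arm risk is p_v = p(1 − VE), and HR = ln(1 − p_v)/ln(1 − p). With n per arm, events are D = n(p + p_v). Freedman's formula is power = Φ(√D (1 − HR)/(1 + HR) − 1.96).
- n = 50, p = 0.7, VE = 0.45: p_v = 0.385, HR = 0.404, D = 54.25; power = Φ(3.128 − 1.96) = 87.9% (stated 88%).
- n = 60, p = 0.6, VE = 0.45: p_v = 0.33, HR = 0.437, D = 55.8; power = Φ(2.926 − 1.96) = 83.3% (stated 83%).

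All 18 cells agree within 0.5 point, so Table 8 is a correct 1:1 calculation. One-sided 5% does not fit. Reading VE as 1 − HR gives only about 61-64% for these two cells, so the table's VE is on the risk-ratio scale.

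**The named comparisons at 2:1.** With k = 2 vaccine recipients per control and n_c controls, D = 2n_c·p_v + n_c·p, and Freedman's form becomes power = Φ(√(kD) (1 − HR)/(1 + k·HR) − 1.96).
- 50:25, p = 0.7: D = 36.75; Φ(2.828 − 1.96) = 80.7%.
- 60:30, p = 0.6: D = 37.8; Φ(2.612 − 1.96) = 74.3%.

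Freedman's formula is the most favourable of the methods tried. Schoenfeld's formula, a two-proportion test and a log-rank simulation (8,000 runs, exponential infection times) give, at VE 45%:

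| Vaccine:control | Rate | Stated (1:1) | Freedman | Schoenfeld | Two proportions | Simulation |
|---|---|---|---|---|---|---|
| 50:25 | 0.7 | 88 | 80.7 | 73.6 | 74.4 | 78 |
| 60:30 | 0.6 | 83 | 74.3 | 67.0 | 69.0 | 72 |
| 70:35 | 0.7 | 96 | 91.7 | 86.6 | 87.7 | 90 |
| 70:35 | 0.6 | 89 | 80.5 | 73.6 | 75.7 | 78 |

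The loss is not produced by switching formula. At 50 per arm and rate 0.7, going from 1:1 to 2:1 takes Freedman from 87.9% to 80.7%, Schoenfeld from 91.6% to 73.6%, and simulation from 91.0% to 78.5%. At 60 per arm and rate 0.6 the moves are 83.3% to 74.3%, 87.1% to 67.0%, and 86.6% to 72.1%.

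**Pooled control.** 3a + 3b = 35 + 35 = 70, falling to 50 or 60 with dropout. That is the 1:1 case, and it returns 87.9% and 83.3%.

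**The case against.** The strongest reply is that Section 13 intends a single control group. Three groups of 70 make 210, the labels 3a and 3b suggest two halves of one arm, and Section 13.1.1 uses the singular. On that reading 88% and 83% are right. This stands as arithmetic. A reader might infer that the stated power is simply not delivered, but the documents do not support so flat a conclusion, because Section 13.1.2 leaves the comparator open. The reply does not remove the problem: pooling is nowhere stated for efficacy, it conflicts with the controls named in Section 3.1, and the sentence about each arm would still be wrong.

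It can also be said that pooling would do little harm to efficacy. The third dose was given in all arms in September 2018, follow-up for infection starts there, every arm receives artemether/lumefantrine beforehand, and randomisation is stratified by village. Blinded infection was similar by cohort in Table 5: 53 of 101 (52%) and 51 of 103 (50%). That is fair. No bias of known size is shown, and the objection to pooling is that it is unstated and partly non-randomised.

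Dropout may also be lighter than planned, since 101 and 103 of 105 per cohort received the third dose. That is not end-of-season retention. Even with no dropout, own-control power is about 87-92% at rate 0.7 and 74-81% at rate 0.6, against 96% and 89% in the table's own rows for 70.

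Three further inferences are tempting and should not be drawn:
- Table 4's 550 and 281 adverse events do not measure bias from a pooled control. They count all events, and Section 1.7.1 attributes the gap to longer follow-up. Section 13.1.1 compares proportions of solicited events, related events and SAEs.
- The 90% chance of seeing an event with rate 0.033 is correct for each vaccine arm of 70. Recomputing it for 35 saline recipients shows no loss in detecting vaccine reactions.
- No single detectable difference between regimens follows from the documents. It depends on retention and background rate, and no objective calls for a formal test of one regimen against the other.

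**Conclusion.** The point holds for the comparisons that the design names. At VE 45%, Arm 1 against 3a or Arm 2 against 3b has about 74-81% power where 88% is stated, and about 67-74% where 83% is stated. Every formula loses at least 7 points. The stated figures apply only to one vaccine arm against 3a and 3b pooled, a comparison that the efficacy section does not specify. The underlying defect is therefore an unnamed comparator together with a power table for an allocation that the design does not use.

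The sizes rest on a two-sided 5% level, VE as 1 minus the risk ratio, and the planned dropout applying equally to vaccine and control arms. The consequence is bounded: efficacy is a secondary objective, main-phase dosing is complete, and no estimate changes because a power figure is restated. The choice of comparator does affect the estimates, so it is the more important repair.

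**What to change.** 1. In Section 13.2, replace the sentence on seventy per arm with 70 vaccine and 35 control per regimen.
2. Recompute Table 8 at 50:25, 60:30 and 70:35. State alpha, sidedness, and that VE in the table means 1 minus the risk ratio. Carry the new figures to the booster paragraph.
3. State in 13.1.1 and 13.1.2 that Arm 1 is compared with 3a and Arm 2 with 3b.
4. Stratify any analysis that pools 3a and 3b by randomisation cohort (1/3a, 2/3b). Keep the equal-arm power figures, if at all, only under a pooled-control label. Note there that they ignore cohort: once a single-regimen comparison is stratified, the other cohort holds no recipients of that regimen, and only its own control contributes.
5. In 13.1.4, note that Arms 1 and 2 were not randomised against each other, so a direct comparison of the two for regimen selection is not a randomised one.

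The cost is wording and one recomputed table. The stated power becomes less favourable, and no subjects, visits or data are added.

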It is known that humans can be protected against malaria by repeated immunization with radiation-attenuated sporozoites. Sanaria, Inc. has developed a process for manufacturing, in compliance with current Good Manufacturing Practices (cGMPs) aseptic, purified, radiation-attenuated cryopreserved sporozoites from a well-characterized isolate of *Plasmodium falciparum* (Pf) (Hoffman et al., 2010). This product, which is called PfSPZ Vaccine, can be administered by needle and syringe.

A collaboration among the Malaria Research and Training Center (MRTC, Mali), the Laboratory of Malaria Immunology and Vaccinology (LMIV) National Institute of Allergy and Infectious Diseases (NIAID), and Sanaria, Inc. (Sissoko et al., 2017) has shown that sterile protection against naturally occurring malaria infection can be achieved. In this study, five doses of 2.7×10^5 PfSPZ during the dry season resulted in protective efficacies of about 48% by time to first positive blood smears (BS) and about 29% by proportion of participants with at least one positive BS during a full malaria transmission season (20 weeks), higher than those reported for other malaria vaccine candidates (Sissoko et al., 2017).

A follow up study in 2015 (ClinicalTrials.gov Identifier: NCT02627456) that reduced the number of vaccinations (from 5 to 3) while increasing the dose of sporozoites at each vaccination (2.7×10^5 to 1.8×10^6 PfSPZ Vaccine) was conducted. Preliminary results show that 42 of 55 (77.8%) participants from the placebo group and 32 of 54 participants (58.1%) from the vaccine group developed Pf infection. Per protocol, the vaccine efficacy (VE) was 51% ($p=0.004$, 95% CI 20-70) by time-to-infection analysis (intention to treat [ITT] 39%, $p=0.033$) and 24% ($p=0.031$, 95% CI 2-41) by proportional analysis (ITT 22%, $p=0.041$), similar to the previous study.

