13.1.2 Vaccine efficacy analysis

Primary efficacy analysis will be based on time to infection, which is defined as the time to the first positive blood smear. Arms will be compared by logrank test for interval-censored data (using the interval package in R). VE will be estimated assuming a Weibull model and allowing for interval censoring and stratification by village (survival package in R).

The proportions of infection will be also compared across arms by the exact binomial test, or the Exact Cochran-Mantel-Haenszel test stratifying on village if needed (using the mantelhaen.test in R with the exact option set to true, this is a conditional exact test). Subjects that are censored prior to the last day of planned follow up will be removed from the analysis and censoring will be assumed to be completely at random. A sensitivity analysis may be performed where all censored subjects are treated as either cases or non-cases in either arm.

Under either of these analyses, we will perform an ITT and a per-protocol analysis. Under the per-protocol analysis, subjects that drop out prior to receiving the full number of vaccinations will not be included in the analysis.

The same efficacy analyses will be performed at the end of the main phase and the end of the booster phase.

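### Table 8 reads VE as a cut in the proportion infected; on the time-to-infection scale of the primary efficacy analysis, the stated 88% power at VE 45% is about 61–63% even with equal arms

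*Combined protocol and SAP*

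**What the plan says.** Section 13.2 sizes the trial mainly on vaccine efficacy. Its headline is "With 50 samples per arm, the study is capable of detecting the protective efficacy of vaccine with 88% power if VE is 45" percent with a background rate of 0.7. A second sentence gives 83% power with 60 per arm, VE 45% and a background rate of 0.6. The supporting Table 8 is titled "Power for group-wise comparison based on logrank test on time to infection". Nothing in the section says whether VE there is a reduction in hazard or in the proportion infected, and alpha is not stated. The section adds that the calculation should roughly carry over to the booster phase.

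Section 13.1.2 sets the analysis: "Primary efficacy analysis will be based on time to infection, which is defined as the time to the first positive blood smear". For the estimate, "VE will be estimated assuming a Weibull model and allowing for interval censoring and stratification by village". The proportion infected is a further analysis: "The proportions of infection will be also compared across arms by the exact binomial test".

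The Precis keeps the two scales apart when it describes the first earlier Mali trial, whose regimen "resulted in protective efficacies of about 48% by time to first positive blood smears (BS) and about 29% by proportion of participants". Section 1.4.3.1 confirms that the time-to-event figure comes from a Cox hazard ratio (48.27%, 95% CI 14.45 to 68.72). For the second trial, section 1.4.3.3.2 gives 51% (95% CI 20 to 70) by time to infection and 24% (2 to 41) by proportion.

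**The concern.** When 60–70% of controls become infected, the same vaccine effect gives very different numbers on the two scales; the earlier trials' 48% against 29% and 51% against 24% show this. A power table titled as a logrank test on time to infection, beside a primary efficacy analysis of time to infection, will be read as using time-to-infection VE. On that reading 45% looks slightly cautious next to 48% and 51%. If the table uses the other scale, 45% is an optimistic assumption, and the quoted power belongs to a larger effect than the reader supposes.

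This affects interpretation. Section 13.2 rests the sample size on this calculation for both phases, and section 13.1.4 uses the efficacy results to help choose a regimen for later studies. Someone told that power is 88% may take a non-significant comparison as evidence against a regimen, when a regimen with a time-to-infection VE of 45% would often miss significance.

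**Working it through.** **Inputs.** Arm sizes of 50, 60 and 70, background rates p0 of 0.6 and 0.7, VE and stated power come from section 13.2 and Table 8. The 70 v 35 allocation per regimen is in section 4.4. Two-sided alpha of 0.05 is an assumption; of the levels tried (also two-sided 0.025, one-sided 0.05 and 0.10) it is the only one that reproduces the table.

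**Step 1: reproduce Table 8.** Take VE as a cut in the proportion infected:

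- p1 = p0(1 − VE)
- HR = ln(1 − p1) / ln(1 − p0)
- expected infections E = n(p0 + p1)
- power = Φ[√E (1 − HR)/(1 + HR) − 1.96] (Freedman's logrank formula, equal arms)

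For 50 per arm, p0 = 0.7, VE = 0.45: p1 = 0.385; HR = ln 0.615 / ln 0.3 = 0.404; E = 54.25; power = Φ(3.13 − 1.96) = 87.9%. Stated: 88.

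For 60 per arm, p0 = 0.6, VE = 0.45: p1 = 0.33; HR = ln 0.67 / ln 0.4 = 0.437; E = 55.8; power = Φ(2.93 − 1.96) = 83.3%. Stated: 83.

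All 18 rows agree within 0.5 point. With HR = 1 − VE and the same alpha, no row comes within 2 points under Freedman, Schoenfeld or a two-proportion test; the average shortfall is 23 to 25 points.

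**Step 2: translate between scales.**

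| Background rate | Table 8's 45% expressed as 1 − HR | A 45% hazard VE expressed as a cut in proportion infected |
|---|---|---|
| 0.6 | 56% (HR 0.437) | 34% (p1 = 0.396) |
| 0.7 | 60% (HR 0.404) | 31% (p1 = 0.484) |

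**Step 3: recompute with VE = 1 − HR, equal arms.** Now HR = 0.55 and p1 = 1 − (1 − p0)^0.55. Schoenfeld's version is Φ[√(E/4) |ln HR| − 1.96].

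For 50 per arm, p0 = 0.7: E = 50(0.7 + 0.484) = 59.2. Freedman: Φ(7.69 × 0.45/1.55 − 1.96) = 60.8%. Schoenfeld: Φ(3.85 × 0.598 − 1.96) = 63.3%.

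| Per arm | Background | Stated | Freedman | Schoenfeld |
|---|---|---|---|---|
| 50 | 0.6 | 76 | 53.5 | 55.9 |
| 50 | 0.7 | 88 | 60.8 | 63.3 |
| 60 | 0.6 | 83 | 61.2 | 63.7 |
| 60 | 0.7 | 93 | 68.7 | 71.2 |
| 70 | 0.6 | 89 | 67.9 | 70.4 |
| 70 | 0.7 | 96 | 75.3 | 77.7 |

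Simulated logrank tests with exponential times give 63% for each of the two scenarios quoted in the text. For 50 per arm at 0.7, grouping infections into 13 visit intervals gives 62%.

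**Step 4: the trial's own 2:1 arms.** Table 8's equal arms are a separate fault, but a corrected table has to deal with both. With k = 2, Freedman's formula becomes Φ[√(kE)(1 − HR)/(1 + k·HR) − 1.96].

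For 50 v 25, p0 = 0.7, HR 0.55: E = 25 × 0.7 + 50 × 0.484 = 41.7, so power = Φ(√83.4 × 0.45/2.1 − 1.96) = 50%. Schoenfeld gives 44% and simulation 49%.

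Simulated power for the other cases is about 49% (60 v 30, 0.6), 55–56% (70 v 35, 0.6) and 62% (70 v 35, 0.7). By simulation, 80% power needs a time-to-infection VE between about 54% (70 v 35, 0.7) and 64% (50 v 25, 0.6).

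**Step 5: precision at 70 v 35, HR 0.55.** SE(ln HR) ≈ √(1/d1 + 1/d0).

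- At 0.7: d1 = 33.9, d0 = 24.5, SE 0.265, 95% CI for VE about 8% to 67%.
- At 0.6: d1 = 27.7, d0 = 21.0, SE 0.289, 95% CI about 3% to 69%.

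**The case against.** **Table 8 is computed correctly for what it represents.** If 70% of controls and 38.5% of vaccinees are infected, 50 per arm does give 88%. That stands: the fault is an unlabelled scale that does not match the leading analysis, not a slip in the formula.

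**Section 13.1.2 never writes VE = 1 − HR.** A Weibull fit can report a hazard ratio or a time ratio. True, but neither is a ratio of proportions. With constant hazard the time ratio is 1/HR, so both lead to the same VE. The earlier time-to-event VE was explicitly based on a hazard ratio.

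**The lower rows already show realistic power.** At background 0.7 the VE 0.30 row implies HR 0.559, a hazard VE of 44%, and states 59, 67 and 73% for 50, 60 and 70 per arm. This supports the recomputation. A reader cannot know that those are the relevant rows, however, and the text quotes only the 45% ones.

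**The implied 56–60% is not far outside experience.** On the hazard scale it is 5 to 12 points above the earlier estimates and inside both confidence intervals. On the proportion scale the contrast is sharper: 45% against 29% and 24%.

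**A more favourable scenario is defensible.** Placebo infection in the second Mali trial was 77.8%. At that rate and a hazard VE of 51%, equal-arm power is 79–82% with 50 per arm and 86–88% with 60. That needs both a higher background rate and a higher VE than the headline states. With 50 v 25, E = 25 × 0.778 + 50 × 0.522 = 45.5, and power is 62% (Schoenfeld) to 69% (Freedman).

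**Efficacy is a secondary endpoint of a phase 1 trial, and main-phase vaccination is complete.** Both are true. Section 13.2 nonetheless rests the sample size on efficacy and extends the claim to the booster phase, so the figures still shape how results are read.

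**Conclusion.** The concern holds. Table 8's VE is a reduction in the proportion infected, whereas the primary efficacy analysis estimates VE from time to infection. With VE 45% on the latter scale and equal arms, the two headline figures fall from 88% to 61–63% and from 83% to 61–64%. With the actual 2:1 allocation they are each about 49%, and full retention (70 v 35) gives about 56% to 62%.

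The conclusion rests on three assumptions:

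- The scale and alpha of Table 8 are inferred, but a match on all 18 rows leaves little room for another reading.
- The Weibull VE is taken as a hazard-type measure.
- Converting between scales assumes proportional hazards, with the background rate as the cumulative proportion infected by the end of follow-up.

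**What to change.** In section 13.2:

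- State the VE scale and alpha used in Table 8.
- Recompute the table with HR = 1 − VE and the actual 2:1 arms (70 v 35, and 60 v 30 and 50 v 25 after dropout), with a second column giving the equivalent reduction in proportion infected.
- Replace the 88% and 83% sentences with the new figures. If an attack-rate assumption is kept, label it and state that 45% corresponds to a time-to-infection VE of 56–60%.
- State the time-to-infection VE detectable with 80% power per regimen (about 54% to 64%, depending on retention and background rate) and the expected confidence interval width.
- Reword the booster-phase sentence to refer to the corrected figures.

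In section 13.1.2, state which Weibull parameter defines VE.

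The cost is one recomputed table and a few sentences. Stated power falls; nothing in the conduct of the trial changes.
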